Proposed care models for young adults with diabetes: delivery of clinical care for young adults with diabetes at Newham is led by [name] (a co-applicant) and a close-knit clinical team including specialist diabetes nurses, dieticians and psychologists. This group have a proven track record of quality improvement and service redesign, e.g. in introducing and evaluating Skype-based clinical consultations (the NIHR-funded VOCAL project, PI [name]).

The content of group clinics will be determined by the co-design process, but it is anticipated that it will cover aspects of their clinical care (e.g. blood glucose self-monitoring and control, sick day rules, diabetes complications, how to manage diabetes around an unpredictable lifestyle, promotion of healthy diet and active lifestyle) and social needs (e.g. finding a job, the impact of diabetes on entitlement to benefits, improving resilience and learning stress-management skills).

Similarly, the relative number of group clinic and individual appointments will be decided during the co-design process. However, we present two possible models below, in order to illustrate the potential for group clinics to be offered in addition to, or as partial substitution for, the current model of care at Newham University Hospital.

- CURRENT model: Standard care for young adults with diabetes at Newham includes 4-monthly clinic visits.
- ADDITION model: Implementation of the co-designed group clinics for young people with diabetes who have consented to join this research project could replace the 'CURRENT' clinical model with an 'ADDITION' model that combines current clinical care with additional group clinic care from the co-designed model; up to 5 additional group clinics will be offered.

SUBSTITUTION model: following implementation and iterative revision of the co-designed model, and according
to its success, the ADDITION model could be replaced by a SUBSTITUTION model. The SUBSTITUTION model
is anticipated to deliver some existing elements of current care (e.g. one-to-one clinical consultations at 0 and 12
months) but will replace other planned clinical contacts with the co-designed group clinics, resulting in a care
pathway that offers no other routine clinical contacts and replaces the current one-to-one clinical contacts at 4 and
8 months with group-based clinics. It is anticipated that 4 cohorts of group clinics will run, but this will depend on
recruitment rates.

Anticipated Output

- Implementation of co-designed group clinics young adults with diabetes
- Transition from CURRENT care to an ADDITION model in which group clinics are additional to existing care.
- Transition of the ADDITION model to a SUBSTITUTION phase where the new care model replaces existing care

Workstream 4: Evaluation of the group clinic-based care model

Operational objective: To conduct a comparative evaluation of the model against standard care to elucidate patient and provider perceptions and mechanisms of action. To perform preliminary analysis on the potential for group clinics to improve clinical outcomes and patient engagement and/or reduce care costs, in order to inform the design of definitive future studies (workstream 4)

Timescale: Q3-Q11

Setting: evaluation of group clinics will be embedded in their delivery and via collection of clinical data

Participants: those delivering and receiving care in group clinics (group clinic participants, n=80-100) and in standard care control data participants, n=60)

(i) Qualitative evaluation

Methodological approach: the researcher-in-residence will conduct a rigorous evaluation of how the group clinics work in practice, identifying their active ingredients, mechanisms of action, enablers and constraints. They will evaluate the experience of the patients using the new service and the staff providing it, using a selective case study methodology. Comparative case studies in traditional services will allow the relative merits of the new service to be better understood, given the established evidence that improvement interventions are more successful when practitioners can see a relative advantage over current practice (27). The embedded researcher will bridge the qualitative evaluation and the economic/quantitative evaluations, helping to feed practitioner views into the design and conduct of these evaluations and to feedback early findings to other stakeholders. At all times, the researcher will adopt a process-oriented and formative approach to the evaluation, negotiating the analysis and interpretation of the emerging evidence and maximising the impact of the interventions.

Data collection: Data will be collected through individual and group interviews with service users and group facilitators; observations of a sample of group clinics and standard care; and documents produced during co-design sessions, steering group meetings, group clinics and the daily lives of participants, including photos and other visual representations (e.g. diagrams, drawings). Data collection proformas and prompts will be informed by our research questions, draft logic models and hypotheses about active ingredients and mechanisms of change (e.g. peer support, vicarious learning, going beyond health needs to tackle wider social determinants). The data collected via interviews in the co-design phase will be combined with the evaluation data as appropriate.

• Individual and group interviews: Interviews will be conducted with a sample of service users including those who drop out of the groups and those who receive standard care. Sample size will be determined by data saturation and is expected to comprise between 20 and 30 participants. Purposive sampling will ensure variation in salient characteristics including type of diabetes, type of clinic attended, ethnicity and language. Group interviews will be conducted with all group clinic facilitators and practitioners delivering standard care. Photos will be used to stimulate discussion and co-creation of data. Interviews will be audio-recorded and transcribed. Bi-lingual health advocates and research assistants will be used for those who do not speak English or for those who feel more comfortable speaking in their first language.

- Observations of group clinics: All group clinics will be observed using a flexible proforma to aid capture of clinic characteristics such as session content, context, group dynamics, and facilitation style. A sample of standard care consultations will be observed as a point of comparison of content and interaction between patient and clinician.
- Documents: All documentation produced during co-design sessions, steering group meetings and group clinics will be collected for analysis. Service users and group facilitators will also be asked to document their experiences inside and outside of clinics using cameras and/or reflective journals.

Data analysis: this will be conducted in three main stages (with some iteration between the stages):

Data collection: the principle clinical outcome measures will reflect:

- Biological markers of diabetes control and complications: we will use markers of control and complications that are also benchmarked as key care processes in the National Diabetes Audit (run by the HSCIC). These are: HbA1C (a measure of glycaemia), blood pressure, serum cholesterol, creatinine, albuminuria, foot surveillance, body mass index, smoking. We will also analyse data on retinal screening if this is included in future national audits. These data will also be collected from, (a) individuals recruited as 'control data participants' (n=60) at external units running young adult diabetes clinics, at the Whittington Hospital NHS Trust, and Barts Health NHS Trust (including Royal London, Mile End, Barts and Whipps Cross Hospitals), and (b) national level data from the HSCIC National Diabetes Audit in an age-matched group.
- Routinely-collected data on outpatient hospital activity: The principal measure for both will be Did Not Attend (DNA) rates in outpatient clinic. (currently 28% at Newham University Hospital). It is important to note that attendance at consultant-led, hospital clinics is often seen as a key measure of patient engagement, but its role in evaluating group clinic deserves further investigation. It may be that attendance at group clinics is perceived by both patients and professionals as a reason to decrease the frequency of clinic attendance. So the quantitative analysis of DNA rates for hospital clinics must be interpreted alongside attendance rates at group clinics and the qualitative findings about the optimal role of group clinics for different patients. Another caveat is that the relationship between DNA rates and clinical outcomes may vary when the frequency of hospital clinic appointment visits changes, e.g. reduce from 6 monthly clinics to annual review. As noted above, preliminary quantitative findings will be discussed and the value of each measure will be explored by the qualitative research team in their evaluation. These data will also be collected for unit-level comparison from the young adult diabetes clinics at the Whittington Hospital NHS Trust, and Barts Health NHS Trust (including Royal London, Mile End, Barts and Whipps Cross Hospitals).
- Indirect markers of clinical outcome: data on unplanned hospital admissions and GP attendance frequency related to diabetes in the target group will be collected as part of a costing analysis of resource use.

• Resource use: resource inputs associated with the implementation of group clinics will be recorded on specifically designed staff- and researcher-completed logs. We will measure all relevant staff contact and non-contact time e.g. for delivery of and participation in staff training, group clinic delivery to patients and time take for other associated activities such as note writing. We will also record patient attendance rates at the level of groups and patients. Given the potential complexity of this data collection, we will seek feedback on the design of the logs from a sample of those who will be expected to complete them, provide accompanying written guidance for reference (and training where feasible) on their completion and check completeness and quality of data on an ongoing basis. Broader resource us data related to use of other core services will be extracted from patient records.

Data analysis: there will be two types of quantitative analysis of clinical outcomes and patient activation:

- Intention to treat: simple descriptive statistics will be used to compare clinical outcomes among young adults with diabetes attending the group clinics with controls from the same clinic over the previous year.
- Comparison of baseline characteristics, clinical outcomes and patient activation among patients who receive the intervention (n=80-100) with control data participants (n=60). The first stage of this process will complement the qualitative findings into which patients are most attracted by the idea of group clinics. We will compare baseline socio-demographic and clinical characteristics of those who accept versus those who decline the opportunity to participate in group clinics. We will then use longitudinal data to compare the trajectories of clinical and activation measures over the following year for individuals in the accept vs. decline groups (difference in difference analysis).
- Comparison to external individual (control data participants) and unit-level data using clinical outcome (and indirect clinical outcome) data collected from young adult diabetes clinics at the Whittington Hospital NHS Trust and Royal London Hospitals. This data analysis will inform a future scaled-up cluster-randomised controlled trial of group clinics by (i) testing the feasibility of unit-level data collection, (ii) identifying differences in the case mix of patients attending young adult diabetes clinics, (iii) characterising the clinical and process outcomes of young adults with diabetes under the care of different units.
- Comparison to national clinical outcome and process benchmark data in an age-matched population from the National Diabetes Audit.

(iii) Costs analysis

We will apply national unit costs to all resource use to estimate relevant staffing capital and running costs related to running the standard vs. group clinics at Newham University Hospital. We will then fully describe resource inputs and costs associated with delivering group clinics (e.g. venue, consultancy and staffing costs) and the impact on use and costs of other core services. Data will be presented in both aggregated and disaggregated form, and for different scenarios e.g. group clinic costs according to variations in attendance rates. Using the comparative approach described above for each patient group, we will assess the impact on use of other services and associated costs, and thus the extent to which the group clinic model substitutes for, rather than adds to, standard care. This in turn will provide an early indication of any potential for efficiency savings for the NHS.

Delivery

Qualitative and quantitative evaluation and analysis of costs will be performed by a research team, independent and external to the implementation team, which includes specific expertise in quantitative evaluation of clinical and economic outcomes in diabetes trials, as well as broad experience evaluating studies into other long-term conditions and the health economic impact of new models of care. The research team will also be supported by the Institute of Child Health Statistical Support Service, who will advise on, and quality assure all stages of the quantitative evaluation including study design, analysis and use of study data to inform a future cluster-randomised controlled trial.

Anticipated outputs

- An understanding of the acceptability and feasibility of the group clinic models
- Theories of changes and associated logic models that identify key mechanisms, active ingredients, and potential generalisability.
- Preliminary data on the potential impact of the group model and identification of parameters to include in future larger scale evaluation.
- An understanding of the heterogeneity of different clinics providing diabetes care to young adults and how to incorporate this in the subsequent design of a cluster randomised controlled trial.

Operational objective: To disseminate the outcome(s) of our scoping and realist review, the co-designed new care model and its evaluation to service users and relevant stakeholders and generalise our findings to a wider context

Timescale: Dissemination activities will be arranged at regular time points throughout the project from Q4 onwards. Dissemination events are likely to occur every 4-6 months throughout the duration of the project, but will be guided by the project steering committee and PPI groups. There will be a concentrated phase of dissemination in Q11+12.

Methdological approach, setting, participants: this will be discussed in the following section.

Delivery: The researcher-in-residence researcher will be responsible for disseminating both provisional and substantive learning within the wider stakeholder group of the project throughout the formative evaluation. They will also contribute to all elements of the dissemination of the final project results.

Anticipated outputs:

- We will write regular reports summarising our research activity and outputs, and these will be available via publicly-accessible portals, e.g. institutional websites.
- We anticipate publishing academic papers in peer-reviewed, open access journals. These publications will
 describe the process of co-designing and implementing group clinics for these populations, present our findings
 about the potential for group clinics to improve clinical outcomes and patient engagement and/or reduce costs, and
 discuss the implications and transferability of our findings for other services and populations.

Dissemination and projected outputs

The aims of dissemination for this project include:

- · Sharing findings with participants, user groups and local staff
- Informing the wider stakeholder community (including clinical networks) of the main outcomes
- · Sharing findings with the academic community
- Communicating main messages to policy makers, strategic decision makers and funders.

The products needed to achieve these aims will be very varied. We will prepare user-friendly versions of the main findings, briefing statements, summaries and academic papers, tailored for at a range of different audiences. Some will be local (e.g., Newham centred, and wider pan-London), others national (e.g., Department of Health, NHSE etc), and potentially international (eg, Society for Adolescent Health and Medicine). Academic outputs will include journal articles in, for example, Diabetic Medicine, the NIHR HS+DR journal, and national and international conference presentations. We will use a dedicated project page on the Association for Young People's Health website, set up a project Facebook page and Twitter account.

Dissemination will be an ongoing process throughout the project, including activity at the outset to raise awareness of the project, at the mid-point to keep interest engaged and to feed back to participants, and at the end and beyond to share the main messages. It is anticipated that regular dissemination events will be scheduled, approximately every 4-6 months during the project, and will culminate in final dissemination events in Q36. The team has a wide range of connections that we will draw on for dissemination, covering statutory, voluntary and patient sectors. These include:

Local London-based and Newham networks

- Institution-based: QMUL, UCL, UCLP, University of East London, Barts Health NHS Trust, Newham CCG, Newham Borough Council.
- Newham CCG have agreed to support dissemination activities, via their Patient and Public Engagement
 Officer, [name], and their existing network of Diabetes Champions and community neighbourhoods.
 Their Diabetes champions include individuals who have particular interest in supporting young adults with
 diabetes. [name] has said "it is a great opportunity to get the community involved in an important
 redesign programme", and we intend to establish their involvement in formal PPI activities, e.g. co-design, as
 well as implementation and evaluation and dissemination at each stage. We will also invite patient
 representatives to join our project steering group
- Local Transforming Services Together programme we will regularly update this commissioning group which is signed up to by 4 inner London CCGs and has prioritised young adults.

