- Does the need for close integration with other health care providers, e.g. primary care, impact the feasibility and costs associated with delivering the new care model?

Quantitative evaluation - general principles

A range of quantitative data (clinical, process-driven and economic) will be collected and analysed as part of a mixed methods evaluation in this project. However, definitive evaluation of the impact of group clinics is not possible within this study for several reasons. First, the intervention is not yet sufficiently developed; the intervention will be codesigned at the beginning of the study period; it will then be refined and improved throughout the remainder of the study period. Second, the timescale of our study is not long enough to evaluate the full impact of new behaviours such as increased exercise, diet changes, clinic attendance. Third, our study focuses on in-depth analysis of a relatively small group of patients, so is not powered to detect a small/moderate effect of group clinics. For example, to show a statistically significant improvement in HbA1c results in the 214 patients attending the young adult clinic, the average HbA1c result would have to decrease from 68 to 57mmol/l for people with Type 2 diabetes, and 86 to 79mmol/l for those with Type 1 diabetes; we do not think is a realistic goal within the timeframe of this project. Lastly, there is uncertainty about the most appropriate outcome measures with which to evaluate impact (i.e. we do not know whether traditionally-used outcome measures for diabetes studies will be the most relevant for these populations and for the anticipated effects of this intervention).

With these limitations in mind, the quantitative analysis will instead focus on:

- Detailed, descriptive comparisons of clinical and service-based outcomes in Newham before/after the introduction of group clinics for young adults.
- Comparison of clinical and service-based outcomes (i) at unit level, between comparable services at Newham University Hospital, the Royal London Hospital and the Whittington Hospital, and (ii) at national level, using National Diabetes Audit data to understand heterogeneity and generalisability.
- Assessing the feasibility of collecting clinical, process and cost data at patient- and unit-level to enable the design of a future cluster randomised controlled trial.

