- health advocates will facilitate participation of patients where a language barrier exists, and we will monitor progress and barriers. Although our study will not include any participants under the age of 16, particular attention will also be paid to the needs of those aged 16-18, and those with learning disabilities or other relevant needs.
- Informed consent will be secured in order to access routinely collected NHS data on participants. Subject to approval by the ethics committee, we will also ask participants to consent to long term follow up and appropriate linkage of their data.
- All staff members will have up-to-date Good Clinical Practice qualifications.
- Information governance procedures will be followed and regular data and process audits will take place.

Patient and Public Involvement

Patient and Public Involvement (PPI) is central to the development of this project and for the plans on how it will be executed. PPI has already directly informed the development of the initial idea and will be critical to the design of the group clinics, and the patient community will be closely involved with the project's evaluation. Patients and the local public will also be central to dissemination activities. Proposed PPI activities will strengthen the relevance, accessibility and success of the project.

The **initial proposal and project design** were informed by patients and the public in the following ways:

- A 1-year pilot project was undertaken in Newham exploring scope and feasibility of peer-support groups to
 improve patient engagement and self-management for young people 16-25 years with diabetes. This led to
 suggestions from patients that health and social care needs should be integrated, and that projects should include
 age appropriate content, multi-agency work and increased use of social networks.
- Women receiving antenatal diabetes care at Newham recently completed a peer-support diabetes education programme and identified a clear challenge in accessing structured diabetes care.
- The Association for Young People's Health has an active youth participation strand that has provided messages about the positive contribution of groups in promoting health in vulnerable groups, and collaboration with a young adult living with diabetes has provided expert patient input.

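### The accept-versus-decline difference-in-difference names no pre-entry period, so parallel trends cannot be checked and a transient excess in accepters at entry could read as benefit

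*Protocol*

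**What the plan says.** The analysis is in the protocol, Workstream 4 (ii) Quantitative evaluation, Data analysis, second bullet. That bullet first sets "patients who receive the intervention (n=80-100) with control data participants (n=60" side by side. It then says "We will compare baseline socio-demographic and clinical characteristics of those who accept versus those who decline the opportunity to participate in group clinics". Finally it will "use longitudinal data to compare the trajectories of clinical and activation measures over the following year". The contrast between self-selected groups, and the name of the method, come from the end of that sentence: "for individuals in the accept vs. decline groups (difference in difference analysis".

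Earlier data appear only in other analyses. The first bullet of the same list is a simple descriptive comparison with "controls from the same clinic over the previous year". The section Quantitative evaluation - general principles plans descriptive before/after comparisons at Newham. Neither gives the difference-in-difference a pre-entry period.

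Two passages suggest that earlier routine results may be obtainable. Workstream 3, Proposed care models: "Standard care for young adults with diabetes at Newham includes 4-monthly clinic visits". Approval by ethics committees: "Informed consent will be secured in order to access routinely collected NHS data on participants".

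**The concern.** A difference-in-difference estimates an effect only if the two groups would have changed in parallel without the intervention. Here the groups form by choice, and the same bullet expects them to differ, since it asks who is drawn to group clinics. A window that opens at entry holds nothing from before it, so the assumption cannot be examined.

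The second risk is differential regression to the mean. If people tend to accept when their control is temporarily poor, their later readings fall back without any help from the clinic. If the entry reading is the baseline, that fall counts as effect.

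The protocol plans to publish on the potential for better clinical outcomes and to use these data in designing the cluster-randomised trial. A spurious fall could become an over-optimistic assumed effect there. The advisory group also reviews quantitative findings for harm, and a spurious gain could hide it.

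**Working it through.** **The plan's own figures.** The protocol gives no precision for this analysis. The nearest figures are in Quantitative evaluation - general principles: "the average HbA1c result would have to decrease from 68 to 57mmol/l for people with Type 2 diabetes", a fall of 11, and 86 to 79 in Type 1, a fall of 7, among 214 clinic patients. SD, power and the split by type are not stated, so they cannot be reproduced. With a common SD, a two-sided 5% test and unpaired groups, n is proportional to 1/δ². Then n(Type 2) = 214/(1 + (11/7)²) ≈ 62 and n(Type 1) ≈ 152. The implied SD is about 21.8 at 80% power or 18.8 at 90%. The figures are therefore not shown to be wrong, but they belong to a different comparison.

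**Bias.** Let d be the transient excess in accepters over decliners at the entry reading only, with no true effect.
- Baseline = entry reading: bias = −d (apparent benefit).
- Baseline = mean of entry and three prior readings: bias = −d/4.
- Baseline = prior readings without the entry value: bias = 0.

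**Size under assumptions.** Assumed: between-person SD 18, within-person SD 12, 60 decliners, 80 or 100 accepters. With the entry reading as baseline, SE = 12 × √2 × √(1/n + 1/60) = 2.90 (n = 80) or 2.77 (n = 100). The false-positive rate is Φ(d/SE − 1.96) + Φ(−d/SE − 1.96).

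| d | Bias | False-positive rate, entry baseline |
|---|---|---|
| 1 | −1 | about 6% |
| 3 | −3 | 18-19% |
| 4 | −4 | 28-30% |
| 5 | −5 | 41-44% |
| 7 | −7 | 68-71% |

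A simulation of 4,000 runs per case agrees. For d = 5 the bias was about −5.0 and the rate 42-43% with the entry baseline, about −1.3 and 9% with the four-reading mean, and about 0 and 5% with prior readings only. When both groups rose by 5 the bias was about 0. When only decliners rose by 5 it was about +5.

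**Plausible d.** If a gap between the groups arises from selection on the entry reading itself, the transient part is (1 − r) × gap. For gaps of 5 to 10 and r of 0.6 to 0.8 this is 1 (0.2 × 5) to 4 (0.4 × 10). The rows for 5 and 7 need a stronger mechanism.

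**Precision.** With equal correlation r between a person's readings, Var(post − mean of k prior) = s²[1 + (1 + (k − 1)r)/k − 2r] = s²(1 − r)(1 + 1/k).
- k = 1: 2s²(1 − r).
- k = 2: 1.5s²(1 − r), SE × √0.75 = 0.87.
- k = 3: (4/3)s²(1 − r), SE × √(2/3) = 0.82.

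With assumed s = 21 and r = 0.6, and 100 or 80 accepters against an assumed 60, the SE at k = 1 is 21 × √0.8 × √(1/n + 1/60) = 3.07 or 3.21. The 95% half-width is 6.0-6.3. It falls to 5.2-5.4 with two prior values and 4.9-5.1 with three. The gain is smaller if correlation decays with time.

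**Availability.** Four-monthly visits give up to three in a year. Newham's non-attendance is 28%. If HbA1c were taken at every attended visit, the mean is 3 × 0.72 ≈ 2.2 readings. If attendances were independent, all three would exist for 0.72³ ≈ 37% of people.

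**The case against.** The strongest reply is that this is detail for an analysis plan that is not shown. The protocol never says that the baseline is one reading, and the stated year can be read as a follow-up horizon only. A statistical support service is assigned to advise on design and analysis. The protocol also says that definitive evaluation is not possible and that the comparisons are descriptive.

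Part of this stands. A reader might infer that the protocol fixes a single entry value as baseline. It does not, so the bias result is conditional on that choice. But the only window it gives this analysis looks forward, and a look-back depends on the scope of consent and of the data request. A later analysis plan could not recover readings that were never requested. The caveat about definitive evaluation limits the claims made; it does not make the parallel-trends assumption checkable.

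Four further inferences are tempting and not supported:
- That any high reading at sign-up counts as benefit. Only an excess in accepters over decliners does.
- That earlier HbA1c values are on record for everyone. The protocol does not say that HbA1c is measured at every visit, gives no visit schedule for the external units, and does not show that decliners would consent. No earlier values are indicated for the enablement and diabetes-distress questionnaires (PEI and PAID).
- That falls of 7 and 11 are thresholds for this analysis. They refer to 214 clinic patients by diabetes type.
- That 60 is the number of decliners. Data collection places those 60 control participants at external units, and the number of decliners is not given.

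**Conclusion.** The point holds in a conditional form. The difference-in-difference compares self-selected groups over the year after entry and names no pre-entry period, so parallel trends cannot be checked. If the entry reading is the baseline, a transient excess of d in accepters over the comparator passes in full into the estimate as apparent benefit.

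The direction and the full pass-through are algebra. The sizes rest on assumptions: the SDs, the correlation, the number of decliners and d itself. Selection on the entry reading alone suggests d of about 1 to 4, for false-positive rates of roughly 6% to 30%. The precision gain from earlier readings is secondary: SE × 0.87 with two, × 0.82 with three, and less if correlation decays. It is worth correcting before consent and data requests are settled; it does not undermine the study's qualitative aims.

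**What to change.** In Workstream 4 (ii), Data analysis, add a pre-entry period to the difference-in-difference:
1. Where consent allows, extract routine HbA1c and the other routine markers for both groups from the 12-24 months before entry. State this look-back in the consent wording and the data request. It does not apply to PEI or PAID.
2. Plot and compare pre-entry slopes between accepters and decliners.
3. Report the estimate with the mean of available pre-entry values as baseline, beside the estimate using the entry value. The working assumes that the excess sits at the entry reading alone. A longer one would also raise the last earlier readings, which is a further reason to look at the slopes.
4. If the pre-entry slopes differ, do not interpret the estimate as an effect and do not use it as the assumed effect size for the cluster trial.
5. Report the number of decliners with data and the number of earlier readings per person in each group.

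The cost is protocol wording and a longer look-back in records that must be opened for the following year anyway. No extra visits or patients are needed. The series will be incomplete because of non-attendance and unknown measurement frequency, and decliners may be under-represented because access needs their consent.
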